#### **10.4 Medications and Non-Drug Therapies**

The following medications are **not** permitted during the course of the study:

- Any FIX concentrate other than BAX326
- Immunomodulating drugs other than anti-retroviral chemotherapy  
(e.g.  $\alpha$ -interferon, or corticosteroid agents at a dose equivalent to hydrocortisone greater than 10 mg/day)

A subject who has taken any of these medications will be discontinued from the study.

#### **10.5 Subject Diary**

A subject diary will be provided to each subject or the subject's legally authorized representative:

- At screening/at all the following study visits, ie, every 3 months  $\pm$  1 week, except the study completion/termination visit

The subject diary will be used to record the following information:

- Infusion record of IP (date, time of the infusion, number of units infused, number of vials utilized, lot number, and reason for infusion [bleeding episode, or prophylactic infusion])
- Details of bleeding episodes (site, type, and severity of bleeding) and response to treatment as described in Section 11.3 "Hemostatic Efficacy"
- All AEs will be recorded that do not fall within the provisions of Section 12.3 "[Untoward Medical Occurrences Not Considered Adverse Events](#)".
- Concomitant medications taken (including immunizations) and non-drug therapy
- Drug accountability (number of unused vials of IP remaining in the subject's refrigerator will be recorded, prior to each study visit).

Subjects and/or their legally authorized representatives will be trained on use of the diary. The diary will be returned to the investigator at interval study visits and will serve as source documentation. At each interval study visit as described above, the subject will turn in a single diary and receive a blank one. The subject diary will serve as a source record and remain at the study site. The currently used paper diary may be replaced by an electronic diary.

**Note:**

**It is crucial that the investigator evaluates and discusses with the subject at each study visit whether the subject adheres to the prescribed treatment regimen for prevention, if applicable, and treatment of bleeding episodes, and whether the subject has correctly entered all necessary information. The investigator will review the diary for completeness, ask for missing information, and enter the examined data on the eCRFs. Any unclear or implausible information should be immediately clarified with the subject at each study visit and instructions related to treatment and data entry be reinforced.**

The investigator will review the AE and concomitant medication record, the number of infusions used to treat bleeding episodes and the corresponding efficacy rating and discuss it with the subject, and enter the information on the appropriate eCRF. For example, if a subject writes in the diary that he or she has taken paracetamol but no AEs are entered, the investigator should ensure that the corresponding condition (eg, headache) is also recorded.

## **10.6 Subject Completion/Discontinuation**

A subject is considered to have completed the study when he/she ceases active participation in the study because the subject has, or is presumed to have, followed the protocol. Reasons for completion/discontinuation will be reported on the Completion/Termination eCRF, including:

- Completed
- Eligibility criteria not met
- Screen failure
- AE
- Discontinuation by subject (eg, withdrawal of Informed Consent, lost to follow-up [defined as 3 documented unsuccessful attempts to contact the subject], dropout)
- Physician decision (e.g., pregnancy, progressive disease, non-compliance with IP/protocol violation(s), recovery)
- Study terminated by sponsor
- Any reason as specified in Section 9.3 “Withdrawal and Discontinuation”
- Or other (reason to be specified by the investigator, eg, technical problems)

Regardless of the reason, all data available for the subject up to the time of completion/discontinuation should be recorded on the appropriate eCRF. Refer to Section 9.3 for reasons for premature discontinuation or withdrawal.

Every effort will be made to have discontinued subjects complete the study completion/termination visit. Assessments to be performed at the termination visit (including in cases of withdrawal or discontinuation) can be found in Supplement [21.2](#) Schedule of Study Procedures and Assessments and Supplements [21.3](#) (Clinical Laboratory Assessments for Transition Subjects) and [21.4](#) (Clinical Laboratory Assessments for Newly Recruited Subjects). The reason for discontinuation will be recorded on the eCRF, and data collected up to the time of discontinuation will be used in the analysis and included in the clinical study report. All unused IP provided to the subject will be returned to the study site.

In the event of subject discontinuation due to an AE, clinical and/or laboratory investigations that are beyond the scope of the required study observations/assessments may be performed as part of the evaluation of the event. These investigations will take place under the direction of the investigator in consultation with the sponsor, and the details of the outcome may be reported to the appropriate regulatory authorities by the sponsor.

## **10.7 Procedures for Monitoring Subject Compliance**

Subject compliance with the treatment regimen and study visits will be monitored by direct review of the subject's source data at the sites and evaluated against the protocol requirements. Additionally, electronic edit checks will be performed on all protocol-specified treatment data that is collected to ensure the quality and accuracy of the data.

## 11. ASSESSMENT OF EFFICACY

### 11.1 Determination of FIX Activity

For the determination of IR and PK at regular study visits, as described in the sections below, the following procedure should be followed:

Subjects will be infused with  $75 \pm 5$  IU/kg of BAX326. Upon completion of the infusion, the butterfly catheter should be flushed with at least 2 mL of saline solution. For the determination of FIX activity, only vials of 500 IU potency from one lot/infusion should be used.

The actual vial potency will be used to calculate the total units administered.

**Note:**

- **In subjects  $\geq 12$  years of age, vials should be rounded up or down to the nearest whole vial.**
- **In subjects  $< 12$  years of age, the total calculated dose should not be rounded up or down to the nearest whole vial in case a dose of  $75 \pm 5$  IU/kg cannot be reached.**
- **In subjects receiving standard or modified prophylaxis, the individual subject's treatment and dosing regimen will be used for IR determination during the optional additional visits. The total dose and potency of the vials used for IR determination will be consistent with the vials used for routine (home) treatment (ie, any potency may be administered).**

#### 11.1.1 Determination of Incremental Recovery Over Time in Subjects Transitioning from BAX326 Pivotal or BAX326 Pediatric Study

FIX levels to determine IR will be assessed at the following visits:

- At screening
- Every 3 months  $\pm 1$  week
- At study termination/completion

Subjects will be infused with  $75 \pm 5$  IU/kg of BAX326. Upon completion of the infusion, the butterfly catheter should be flushed with at least 2 mL of saline solution. All assessments should be done at least 5 days after the previous dose of BAX326, and the subject must not actively bleed. The procedures for blood sampling are described in Section 11.1.6.

**Table 11.1-1**  
**Time Points of Determination of FIX Activity**

Assessment of recovery	Pre-infusion	0-30 minutes prior to infusion
	Infusion of $75 \pm 5$ IU/kg BAX326	
	Post-infusion	30 minutes $\pm 5$ minutes

The sample for measurement of FIX activity will be obtained from an extremity different from that used for the infusion of IP.

### **11.1.2 Determination of PK for PK-Tailored Dosing**

An abbreviated PK will be performed in subjects who will receive a PK-tailored dosing and who have not undergone a PK study either in BAX326 Pivotal 250901 or BAX326 Surgery 251002. Blood samples for the PK evaluation will be collected at the time points shown in [Table 11.1-2](#).

**Table 11.1-2**  
**Time Points for Measurement of FIX Activity for PK Assessment**

Pre-infusion	0-30 minutes prior to infusion
Infusion of $75 \pm 5$ IU/kg BAX326	
Post-infusion	30 $\pm 5$ minutes
	9 $\pm 3$ hours
	24 $\pm 6$ hours
	48 $\pm 6$ hours
	72 (- 6) hours

Note: The PK assessment must be performed at least 5 days (120 hours), preferably 7 days, following the previous dose of a FIX product and the subject must not actively bleed.

Samples for measurement of FIX activity taken through 6 hours post-infusion will be obtained from an extremity different from that used for the infusion of IP, using a 21- or 23-gauge thin-walled needle. Where needed, the phlebotomy site will be kept patent via an infusion of normal saline. In this event, at least 2 mL of blood will be collected and discarded before collection of the next test sample into a fresh syringe.

If the subject has a central venous catheter, the central line should be used to administer the infusion and a peripheral venipuncture should be used to collect the blood samples. In the event that a blood sample must be drawn through the central line used for administration of IP, the line must first be flushed with 5 mL normal saline or other suitable catheter flush solution that does not contain anticoagulant. At least 5 mL of whole blood must be collected and discarded prior to obtaining the sample.

### **11.1.3 Determination of Incremental Recovery Over Time in Newly Recruited Subjects and Subjects Receiving a PK-Tailored Dose**

FIX levels to determine IR will be assessed at the following visits:

- At ED1 (only newly recruited subjects)xxi
- At Week 4 ± 1
- At Month 3 ± 1 week
- Every three months ± 1 week
- At study termination/completion

---

**Table 11.1-3**  
**Time Points for Measurement of FIX Activity for IR Assessment**

Pre-infusion	0-30 minutes prior to infusion
Infusion of BAX326, at dose of $75 \pm 5$ IU/kg or at the subject's individual PK-tailored dose, whichever is higher	
Post-infusion	30 minutes ± 5 minutes

Samples for measurement of FIX activity will be obtained from an extremity different from that used for the infusion of IP.

---

xxi For newly recruited subjects planned to receive a PK-tailored dose regimen ED1 corresponds to the PK visit.

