### 8.1.3 Subjects Receiving PK-Tailored Prophylaxis

Subjects who will receive a PK-tailored dose regimen will undergo an abbreviated PK study with 1 pre- and 5 post-infusion sampling timepoints up to 72 hours following the infusion of  $75 \pm 5$  IU/kg BAX326 to determine FIX activity levels (ie, within 30 minutes pre-infusion, and  $30 \pm 5$  minutes,  $9 \pm 3$  h,  $24 \pm 6$  h,  $48 \pm 6$  h and  $72[-6]$  h post-infusion). Also, blood samples for the determination of TGA parameters will be taken at the same time points. Based on the subject's individual PK, the dose and frequency will be determined to ensure that FIX activity levels in plasma of at least 1% above the subject's individual FIX level observed at baseline are maintained. The maximum dose is 120 IU/kg. Doses higher than 120 IU/kg are not allowed and therefore frequencies requiring a higher dose are excluded. Subjects continuing from the continuation study and newly recruited subjects with confirmed eligibility will receive BAX326 at a dose regimen as determined by the investigator until the dose and frequency, calculated by the sponsor, are available at the study site. Upon availability of the PK-tailored treatment regimen, the subject will start the PK-tailored treatment 4 weeks  $\pm 1$  prior to the respective next 3-monthly visit. Bleeding episodes will also be treated with BAX326.

Hemostatic efficacy assessments will be performed at the respective next 3 monthly visit after start of the PK-tailored treatment regimen as well as at any subsequent 3 monthly visit. At these same time points, pre- and post-infusion FIX activity levels as well as pre- and post-infusion TGA parameters, if applicable, will be determined to evaluate the potential correlation between pre-infusion FIX levels, TGA parameters and the occurrence of bleeding episodes. In newly recruited subjects, immediately prior to the first infusion of BAX326 a blood sample for FIX inhibitor determination will be drawn. The study site will call the subjects after  $8\pm 1$ ,  $17 \pm 1$  and  $22 \pm 1$  weeks of start of treatment to discuss the potential occurrence of bleeding episodes and/or AEs.

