## 11.2 TGA Testing

Blood samples for TGA testing will be taken at the same time points as for FIX activity determination in a subset of subjects. Subjects will be infused with  $75 \pm 5$  IU/kg of BAX326 during the regular study visits. Upon completion of the infusion, the butterfly catheter should be flushed with at least 2 mL of saline solution. The same criteria as described in Section 11.1 for determination of FIX activity also apply for TGA testing. TGA testing will only be performed in subjects 12 years and older.

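### For PK-tailored subjects the visit infusion shared by incremental recovery and TGA has two stated doses, and the exploratory ED1-to-end-of-study TGA change does not allow for it

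*Protocol*

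**What the plan says.** **Recovery infusion.** Protocol 11.1.3 covers newly recruited subjects and all subjects on a PK-tailored dose. Its Table 11.1-3 gives 75 ± 5 IU/kg or the dose "at the subject's individual PK-tailored dose, whichever is higher". Its visit list runs from ED1 through the 3-monthly visits to the last one: "At study termination/completion".

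**Cap on the tailored dose.** Section 8.1.3: "Doses higher than 120 IU/kg are not allowed and therefore frequencies requiring a higher dose are excluded". Section 8.6.3.1.1 repeats 120 IU/kg. Section 6.1, where it introduces PK-tailored treatment, still gives a ceiling of 100 IU/kg.

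**TGA infusion.** Section 11.2 draws TGA samples at the FIX activity time points. Section 11.2.2 concerns subjects aged 12 or over on PK-tailored prophylaxis and lists ED1 (for some transitioning subjects), Week 4, Month 3 and Month 6. Its Table 11.2-2 gives 75 ± 5 IU/kg with no alternative.

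**Flow diagram (Table 21.1-1).** Item 6 (3-monthly visits) and item 8 (termination) each describe one infusion serving both recovery and TGA, at 75 ± 5 IU/kg.

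**ED1.** The footnote to 11.1.3 says: "For newly recruited subjects planned to receive a PK-tailored dose regimen ED1 corresponds to the PK visit". Table 11.1-2 sets that infusion: "Infusion of $75 \pm 5$ IU/kg BAX326". Item 3 of the flow diagram gives the same dose for an ordinary first infusion.

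**Analysis.** Table 21.4-1 schedules TGA at ED1 and at termination for newly recruited subjects. SAP 11.2 summarises TGA at both visits, the pre-to-post percent change at each, and, for newly recruited subjects, the percent change from ED1 to end of study. It does not say which sample that last change uses, and none of these summaries has a dose condition.

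**The concern.** One infusion supplies both the recovery and the TGA samples, so it can have only one dose. A site treating a subject tailored above 80 IU/kg departs from one table whichever dose it gives, and sites may choose differently.

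Recovery is divided by dose, so it is protected to first order. TGA parameters are not. If a newly recruited PK-tailored subject is infused at 75 ± 5 IU/kg at ED1 and at a higher tailored dose at the end, a change in post-infusion TGA mixes a dose difference with any change over time. A reader of the SAP 11.2 table could not separate the two.

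**Working it through.** The plan states no figure to reproduce: the sample size has no statistical basis and every analysis is descriptive.

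**1. Can both rules be met?** The fixed rule allows 70 to 80 IU/kg. The higher-of rule requires the tailored dose once that exceeds 75 ± 5. Above 80 IU/kg the two do not overlap.

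**2. Does the more specific text settle it?** At Month 3 and Month 6, sections 11.1.3 and 11.2.2 both apply by name to PK-tailored subjects, so neither is the more specific. At termination 11.2.2 is silent, and the conflict is Table 11.1-3 against item 8.

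**3. Dose ratio, end of study over ED1.**

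| End-of-study dose | ED1 at 70 | ED1 at 75 | ED1 at 80 |
|---|---|---|---|
| 120 IU/kg | 120/70 = 1.71 | 120/75 = 1.60 | 120/80 = 1.50 |
| 100 IU/kg | 100/70 = 1.43 | 100/75 = 1.33 | 100/80 = 1.25 |

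With 75 ± 5 at both visits the ratio stays between 70/80 = 0.88 and 80/70 = 1.14.

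**4. Expected FIX rise.** Rise = recovery × dose. At the pivotal median recovery of 0.88 (protocol 6.4.1):
- 75 IU/kg: 0.88 × 75 = 66 IU/dL
- 100 IU/kg: 0.88 × 100 = 88 IU/dL
- 120 IU/kg: 0.88 × 120 = 105.6 IU/dL

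For scale, pivotal mean recovery moved from 0.87 to 0.95 at the repeat PK (section 6.1), a ratio of 1.09. Calculated recovery is unchanged by dose: 105.6/120 = 66/75 = 0.88.

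**5. Who would be tailored above 80 IU/kg?** Assume one compartment, steady state and a trough 1 IU/dL above baseline. Then dose D = (2^(τ/T) − 1)/IR, where τ is the dosing interval, T the half-life and IR the recovery, so T = τ/log2(D × IR + 1).

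| Interval, recovery | T at D = 80 | T at D = 120 |
|---|---|---|
| 168 h, 0.88 | 27.3 h | 24.9 h |
| 168 h, 0.53 | 30.9 h | 27.9 h |
| 168 h, 1.35 | 24.8 h | 22.9 h |
| 96 h, 0.88 | 15.6 h | 14.3 h |
| 96 h, 0.53 | 17.6 h | 16.0 h |

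The pivotal half-life had median 24.58 h and minimum 15.83 h. Doses of 80 to 120 IU/kg are therefore plausible with weekly tailored dosing and rare with twice-weekly dosing. SAP 6.6 judges PK-tailored compliance on a 6-8 day interval; protocol 6.1 expected twice weekly to be the most common.

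**6. What if the higher-of rule were deleted?** Take a weekly subject tailored to 120 IU/kg and infused at 75 IU/kg at the visit, with no further dose until the next scheduled infusion. With negligible carry-over, the following trough rise is 75/120 = 0.63 of the target of 1% above baseline (70/120 = 0.58 to 80/120 = 0.67 over the window).

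**The case against.** The strongest reply is that 11.1.3 is the specific rule for these subjects and overrides general text. Much of that stands.

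- A reader might count the synopsis and sections 11.1, 11.1.1 and 11.2 as further contradictions. They are general statements. Section 11.1 introduces its dose with "For the determination of IR and PK at regular study visits, as described in the sections below, the following procedure should be followed", and section 11.2 sets 75 ± 5 "IU/kg of BAX326 during the regular study visits". These need a cross-reference to 11.1.3, no more.
- A reader might add flow item 4a, the Week 4 visit of newly recruited subjects. Tailored treatment starts 4 ± 1 weeks before a 3-monthly visit counted from ED1. With 30-day months that is day 55 at the earliest (90 − 35) and day 69 at the latest (90 − 21) for the first such visit, after Week 4 ± 1. No conflict is shown there.
- Quoting 1.6 alone would overstate certainty, because section 6.1 implies 1.33.

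The reply does not dispose of Table 11.2-2, which is as specific as Table 11.1-3. And if Table 11.1-3 does prevail at termination, the dose difference between ED1 and end of study becomes planned, which makes the silence in SAP 11.2 matter more.

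The effect on the analysis is also heavily conditional: a newly recruited, PK-tailored subject, tailored above 80 IU/kg, with TGA at both visits, and a change taken on post-infusion values. SAP 5 reports that only adults had the abbreviated PK, which narrows the group further. That is fair, and it fixes the grade.

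**Conclusion.** The protocol is wrong as written: the same visit infusion carries two doses for PK-tailored subjects, and above 80 IU/kg they cannot both be followed. The point is minor.

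Its analytic reach is limited to exploratory, descriptive TGA output. The clearest case is the ED1-to-end-of-study change in newly recruited subjects, if it uses post-infusion values; the dose ratio within a subject can then reach 1.6, or 1.33 under the section 6.1 ceiling. The end-of-study post-infusion summaries also mix doses, but that adds little to existing spread: at a fixed 75 IU/kg, recoveries of 0.53 to 1.35 already give rises of 39.8 to 101.3 IU/dL, a 2.5-fold range.

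A reader might infer that recovery over time or the trial's main results are compromised. The documents do not support this. Recovery is divided by dose in SAP 9.1, pre-infusion TGA precedes the infusion in question, and the primary, safety and bleeding-rate results do not use these samples.

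The number of affected subjects and the response of TGA to dose are not in the documents. The half-life ranges rest on the one-compartment assumption and are illustrative.

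**What to change.** 1. **Protocol.** Keep the higher-of rule in Table 11.1-3 and carry it into Table 11.2-2 and flow items 6 and 8. Add a cross-reference to 11.1.3 in the synopsis and sections 11.1, 11.1.1 and 11.2. Settle the ceiling by changing 100 to 120 IU/kg in section 6.1, if 120 is intended. Do not resolve the conflict by deleting the higher-of rule, because that would under-dose weekly subjects against their own trough target.
2. **SAP 11.2.** State that the ED1-to-end-of-study TGA change uses pre-infusion values. For any post-infusion change, show subjects infused at a tailored dose above 75 ± 5 IU/kg in a separate row, or list them with the infused IU/kg.

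The cost is a few lines of protocol wording and two sentences in the SAP. No new data are needed: infused units are recorded (protocol 10.5) and SAP 9.1 already uses dose per kg for this infusion. The downside is smaller cells in one exploratory table. SAP version 2.0 is dated September 2017, after the planned end of participation for most subjects. If the visits are complete, the SAP change is the part that can still act, and the listing of infused dose will show which rule sites followed.

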#### 11.1.4 Additional Determination of Incremental Recovery in Subjects Receiving Standard (Twice Weekly) Prophylaxis

In approximately 20 subjects, FIX activity will be also be determined at 4 additional time points during a 6-month period with regular, twice weekly prophylactic infusions, **without the requirement of a wash-out period**. In subjects aged < 12 years, additional IR determination is optional.

On 2 occasions, FIX activity should be assessed **3 days** after a prophylactic infusion of BAX326, ie, before and after the subsequent prophylactic infusion of BAX326, and on the other 2 occasions 4 days after a prophylactic infusion of BAX326, ie, during the subsequent prophylactic infusion of BAX326, as shown in [Table 11.1-4](#).

---

**Table 11.1-4**  
**Time Points for Determination of Pre- and Post-Infusion FIX Levels**  
**During Regular, Twice-Weekly Prophylaxis**

---

Example: **3 days** after last prophylactic infusion:

Last prophylactic infusion  
approx 72 hours ago  
(eg: Monday morning)

→ Subsequent prophylactic infusion approx 72 hours later  
(eg: Thursday morning):

Pre-infusion	0-30 minutes prior to infusion
Infusion of regular prophylactic infusion	
Post-infusion	30 ± 5 minutes

Example: **4 days** after last prophylactic infusion:

Last prophylactic infusion  
approx 96 hours ago  
(eg: Thursday morning)

→ Subsequent prophylactic infusion approx 96 hours later  
(eg: Monday morning):

Pre-infusion	0-30 minutes prior to infusion
Infusion of regular prophylactic infusion	
Post-infusion	30 ± 5 minutes

### 11.1.5 Additional Determination of Incremental Recovery in Subjects Receiving Modified or PK-Tailored Prophylaxis

In subjects receiving modified prophylaxis, FIX activity levels will also be determined within a 6-month period pre- and post-infusion at 4 different timepoints depending on the frequency of weekly prophylactic infusions **without the requirement of a wash-out period**. The pre- and post-infusion blood draws should occur such that they reflect the individual dosing interval. In subjects aged < 12 years, additional IR determination is not required.

Examples:

- Once weekly infusions: No additional IR determination is necessary, however, the regular study visit should be performed after a wash-out period of exactly 7 days to reflect the regular interval of 7 days.
- Twice weekly infusions: The schedule for blood sampling is described in Section 11.1.4.
- Three infusions per week, eg. Monday – Wednesday – Friday – Monday (2, 2 and 3 days)
  - On 2 occasions, FIX activity should be assessed 2 days after a prophylactic infusion of BAX326, ie, before and after the subsequent prophylactic infusion of BAX326, and
  - on the other 2 occasions 3 days after a prophylactic infusion of BAX326, ie, before and after the subsequent prophylactic infusion of BAX326 (see Table 11.1-4 for guidance).

